## **1. Introduction/Background/Purpose:**

The United Nations has declared that chronic non-communicable diseases such as heart disease and diabetes pose a greater health burden worldwide than do infectious diseases, contributing to 35 million deaths annually (1). The incidence of obesity has risen continuously over the last several decades. According to data from the National Health and Nutrition Examination Survey, the prevalence of obesity among women of reproductive age (20–39-years old) in the United States of America is nearly 31.8% (2). Excessive weight gain during pregnancy and postpartum retention of pregnancy weight gain are significant risk factors for continued obesity later in life (3). Pregnancy is often described as a window to future health, as many women are diagnosed with metabolic conditions for the first time in their life during pregnancy. Obesity syndrome, otherwise known as metabolic syndrome, is associated with the development of chronic diseases, such as type 2 diabetes, chronic hypertension, and heart disease. The underlying causative factor of metabolic syndrome is a state of insulin resistance. Due to physiologic changes that occur during pregnancy, women may be at increased risk for developing insulin resistance during pregnancy making the postpartum period an ideal time to intervene to prevent and treat this epidemic(4).

Although there is a strong desire to lose weight in the postpartum period, many women struggle to actually lose weight. Low carbohydrate diets have been compared with low fat, energy restricted diets, the standard American style diet as recommended by the United States Department of Agriculture Dietary Guidelines for Americans (5-14). A meta-analysis of five trials with 447 participants (13) and a 1-year trial involving 311 obese women (7) suggested that a low carbohydrate diet is a reasonable alternative to a low fat diet for weight loss and may have favorable metabolic effects, including improvement in insulin resistance (14). In addition, it has been reported that compared with a low fat diet, a low carbohydrate diet program had better participant retention and greater weight loss (9).

The X-PERT weight loss program offers a structured patient centered educational program for a low carbohydrate diet through a combination of resources, which include in person group meetings, online educational materials, and printed educational materials (15). Some research has shown that greater weight loss and diet adherence is achieved when there is a behavioral component added to a diet plan (16). For example, it has been reported that weight loss was substantially greater in participants who attended group sessions regularly (17). We propose that a low carbohydrate diet with a behavioral component is associated with improved insulin sensitivity as compared to the standard of care obesity education that is part of routine postpartum care.

## **2. Concise summary of project:**

This trial will be a comparative non-blinded randomized controlled trial in obese postpartum women.

Three groups will be compared during the postpartum period:

1. Control Group: Standard of Care

2. Intervention A: Low carbohydrate diet with printed materials and online resources, provided by X-PERT weight loss program.
3. Intervention B: Low carbohydrate diet with a behavioral component consisting of twelve weekly meetings with an X-PERT trained professional supported with printed materials and online resources.

The number of subjects studied will be 321 subjects at UTMB.

### **3. Study procedures:**

Eligible subjects will be approached, and those who consent will be randomized to one of the three groups described above.

All groups will receive standard postpartum care. In addition, all subjects enrolled in the study will have three study visits at which time a blood and urine sample will be collected. Subjects may be contacted by trained research personnel throughout the study period to remind subjects of upcoming appointments.

Subjects enrolled in the intervention groups (Intervention A&B) will receive printed materials and have access to online resources provided by X-PERT weight loss program throughout the course of the study.

- The printed material is approximately 200 pages in length and includes 12 topic-specific sections with information on nutrition, lifestyle, health, tools and tips for maintaining diet, recipes, and food diary templates.
- The online resource can be accessed by an application on a phone or tablet or through the internet via a computer.
- The online resource includes 12 informational sessions (designed to cover topics in a similar fashion to the group sessions), a digital copy of the printed materials, option to take part in an online form, and the option to record personal health information, such as height, weight, monitoring of health points (such as waist circumference, lab values, etc), carbohydrate intake, eating frequency, and dietary approach.
- Subjects will access the online application via a de-identified study related email address. This email address will be provided to the subject; a personal email address will not be used. In order to access the online application, the subjects will input a study related email address and a password that they chose. The email address will also serve as the username for the online application. The online application has the ability to enter personal information, as mentioned in the previous bullet point. The personal health information can be entered into the online application as often as any subject chooses, including no entry at all. The subjects are not required to enter personal health information into the online application, rather subjects are given the option.

Additionally, subjects enrolled in Intervention B will have 12 weekly group sessions with an X-PERT trained professional. The group sessions will last approximately 1.5 hours and have no more than 20 subjects enrolled in each group. Subjects will be welcome to bring their infant to each group session. A babysitter will not be provided

so the subject will be responsible for taking care of her own infant. Breastfeeding or formula feeding during the group session will be encouraged. The group session is available to research study participants only; besides the infant, no additional family members will be allowed. If enrolled in Intervention B, subjects will have up to 15 in person visits.

Blood and urine samples will be collected at each study visit. The first study visit will occur at 2-3 weeks postpartum. The second study visit will occur at 3 months postpartum (+ 3-week window). The third study visit will occur at 6 months postpartum (+ 3-week window). All samples will be collected while the patient is fasting (not eating for at least 8 hours). A standard 4oz sterile urine collection cup will be provided for each urine sample. Urine will be checked for glucose and ketones by dipstick. Approximately 20mL of blood will be collected with each sample. The blood samples will be used for the following tests:

- Hemoglobin A1c (HgA1c)
- Lipid panel
- Homeostatic Model Assessment (HOMA) test for insulin sensitivity or resistance: we will measure fasting insulin and glucose levels. Fasting will be defined as the last meal more than 8 hours before testing (i.e. overnight fasting). We will be using the following computation to calculate HOMA.

$\text{HOMA-IR} = \frac{\text{Glucose} \times \text{Insulin}}{22.5}$	$\text{HOMA-IR} = \frac{\text{Glucose} \times \text{Insulin}}{405}$
$\text{HOMA-}\beta = \frac{20 \times \text{Insulin}}{\text{Glucose} - 3.5} \%$	$\text{HOMA-}\beta = \frac{360 \times \text{Insulin}}{\text{Glucose} - 63} \%$
Glucose in Molar Units mmol/L	Glucose in mass units mg/dL

Blood and urine samples will be taken to the lab to complete the above-mentioned tests and/or stored at -80°C in our perinatal research department for later processing. The blood and urine will be stored in the perinatal research department with the potential for future metabolic testing that relates to this research study. Only the PI and research staff involved with this study will have access to the stored samples.

All subjects will receive a participant ID number. Data will be collected and stored with the participant ID code only. The master enrollment log linking subject identifiers with study ID numbers will be kept in a password-protected database. Several data collection forms will be used. Data on these forms devoid of personal identifiers will be securely stored at our perinatal research division. The research coordinator and PIs will be available to monitor the data and correct any discrepancies based on source documents if needed.

Data to be collected from each subject via chart review includes: demographics, relevant vital signs (including height, weight, waist circumference, and blood pressure),

obstetrical history, current medications, relevant laboratory results, and other pertinent information as relates to the research study.

For subjects enrolled in Intervention A or B, personal information that is recorded through the online resource will be available to the study team in a de-identified manner compliant to IRB policies. At the time of completion of the study, the principle investigator will receive an encrypted document from the X-PERT information technologist that will include the personal health information that the subjects entered into the application. This information will be provided with the subjects' study related email address which has already been de-identified. This information will be used in the data analysis of the study. Any information involving the online application will not be available to the researchers at the time of study visits.

For subjects enrolled in Intervention B, the X-PERT trained professional leading the group sessions will have access to the personal health information for the subjects' enrolled in their group sessions. The information will be transferred from the X-PERT information technologist to the X-PERT trained professional in an encrypted and de-identified manner. The X-PERT trained professional will not have direct personal health information about the individual participant, rather the X-PERT trained professional will receive data about the total subjects enrolled in the class. The data will be accessible to the professionals at the time of each group session through the completion of the 12-week course.

Health records will be reviewed from initiation of obstetric care through the 6-month postpartum period. Throughout the study period and up to 2 weeks after the final study visit, the principle investigator (PI), co-investigator, and research coordinators will review medical records for outcomes. The subject will be requested to sign a medical records release to obtain medical records if the patient receives care at a non UTMB hospital or clinic.

### **3.1. Study visits/Follow-up**

#### **Screening recruitment and consenting**

##### Screening

Under the direction of the PI, trained research staff will be available to screen and consent subjects according to study protocol. Medical records of all potential subjects with a BMI  $\geq 30$  kg/m^2 (calculated by weight at the final prenatal visit prior to delivery) will be reviewed and those who satisfy inclusion and exclusion criteria will be approached at UTMB and a written informed consent will be obtained. A screening log will be used to track all subjects approached for the study.

The potential subjects that are recruited for the study will be contacted by the PI, co-investigators, or other trained research staff during their postpartum stay in the hospital. There will be no recruitment for the research study prior to birth. Research staff will review patients' electronic medical record. The health care provider of the

potential subjects will be notified that the patient may qualify for this research study. The health care provider will inquire if the patient would like to discuss the study with research personnel. If so, research staff will discuss the study with the patient and invite her to take part in the research study. Subjects will be recruited, enrolled and consented in a private room in order to respect the privacy of potential subjects.

#### Consenting process

Written consent will be obtained by direct person-to-person contact.. The PI, study coordinator, or a collaborator will be responsible for the informed consent. Subjects will be given time needed in order to fully understand and read the consent forms. All efforts will be made by the research staff to answer all questions the subject has and to ascertain that subjects have the right to refuse to participate in the study. As part of the consenting process, an assessment of comprehension and understanding of the English language will be performed. The potential subject will be given a sample of the X-PERT printed document. The potential subject will answer three questions about the sample material. Understanding and comprehension of the English language will be assessed by the research staff consenting the patient for the study. The potential subject will be required to answer all three questions correctly in order to be a potential candidate for the study.

#### Randomization

A confidential computer-generated simple randomization scheme will be prepared and provided on an ongoing basis to our study coordinator. A randomization log with group assignment, subject name and medical record number will be used to track the randomization process.

#### Group assignment/Intervention

Once a subject is consented and randomized, the appropriate intervention according to group assignment will be implemented.

### **Visit #1 at 2-3 weeks postpartum, Visit #2 at 3 months postpartum and Visit #3 at 6 months postpartum.**

All patients will have a blood sample and urine sample collected at each study visit. The blood and urine sample will be collected while the patient is fasting. The fasting period is defined as at least 8 hours without food. The subjects will be allowed to drink water. All subjects will have the option of first morning visits in order to utilize the overnight period as the fasting period.

A standard 4oz sterile urine collection cup will be provided for each urine sample. Urine will be checked for glucose and ketones by dipstick. Approximately 20mL of blood will be collected at each study visit. The urine sample will be assessed for urine glucose and ketones by urine dipstick. The blood samples will be used for the following tests: Hemoglobin A1c (HgA1c), lipid panel, homeostatic Model Assessment (HOMA) test for insulin sensitivity or resistance. The samples will be taken to the lab and/or stored at -80°C in our perinatal research department for later processing for use in the research study.

Subjects' vital signs, including blood pressure, waist circumference, height and weight, will also be recorded.

The data collected will not be used for clinical diagnosis or treatment purposes. Subjects will be reassured that participation in the study is voluntary and will not interfere with diagnosis or treatment of her condition.

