### **3.2. Baseline Procedures**

Routine postpartum care will be provided by the subjects' clinical providers. Trained and experienced research staff will be responsible for all research study procedures and data abstraction.

Several data collection forms will be used during these processes. Data on these forms, devoid of personal identifiers, will be securely stored at our perinatal research division.

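### Study-visit data are barred from clinical use with no exception for a high blood pressure, and no step for telling the woman or her provider is stated

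*Combined protocol and SAP*

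**What the plan says.** Section 3.1, under the heading for Visits 1 to 3, sets out fasting blood and urine sampling and then adds: "Subjects' vital signs, including blood pressure, waist circumference, height and weight, will also be recorded". The rule on use follows directly: "The data collected will not be used for clinical diagnosis or treatment purposes". The next sentence has staff reassure women that "participation in the study is voluntary and will not interfere with diagnosis or treatment of her condition".

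Section 3.2 gives the study procedures to research staff and leaves care elsewhere: "Routine postpartum care will be provided by the subjects' clinical providers". Section 3 lists, among data taken by chart review, "relevant vital signs (including height, weight, waist circumference, and blood pressure". Section 3.4 makes worsening blood pressure a secondary outcome. It is defined by a pressure of at least 140/90 mm Hg, by anti-hypertensive use, or by a dose increase.

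**The concern.** Most study-visit values are laboratory results that may come back later or be run from stored samples, and a rule against clinical use of such data is ordinary. Blood pressure differs. It is known at once, it needs no assay, and a high value in an obese woman who has recently delivered can call for prompt clinical attention.

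The protocol does more than leave the matter open. It states a rule, and taken literally that rule points staff away from acting on any visit value. A high pressure that her provider has not seen elsewhere could then go unacted on because no one has been told to pass it on. Practice could also differ between staff members or, since the trial is not blinded, between arms.

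**Working it through.** No arithmetic applies, because the plan attaches no figure to this point. The check is to set the relevant sections side by side and ask of each whether it carries a high visit reading to the woman or to her provider.

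1. **Scope of the rule (3.1, Visits 1 to 3).** The sentence on clinical use comes straight after the vital-signs line and refers to the data collected without qualification. On its plain reading, blood pressure is covered.
2. **Reassurance (3.1, Visits 1 to 3).** Non-interference with care is a promise not to obstruct. It creates no duty to report.
3. **Provider contact (3.1, Screening).** The one stated contact is about recruitment during the hospital stay: the provider of "potential subjects will be notified that the patient may qualify for this research study". Nothing extends it to later visits.
4. **Records (3).** The stated flow is into the study. Staff review charts, and women are asked to "sign a medical records release to obtain medical records if the patient receives care at a non UTMB hospital or clinic". No flow outward is described.
5. **Chart review (3).** Blood pressure is on the list, so some pressures are in the clinical chart. Whether these include the readings that Section 3.1 says are also taken at visits is not stated.
6. **Study forms (3.2).** Study data go onto forms without identifiers, held in the research division. No section says that a visit reading is entered in the chart or flagged there.
7. **Outcomes (3.4).** The 140/90 limit defines an outcome and has no action attached. The masked review by the principal investigator validates outcomes and is not described as notifying anyone.
8. **Safety monitoring (9).** The collaborators and coordinator are responsible for safety. What is described is a study-level report that summarises adverse events. A high reading is not defined as an adverse event, and no notice about an individual woman is set out.

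**Are high readings foreseeable?** Yes. Section 4 requires a BMI of at least 30 at the last prenatal visit. Section 5 does not name hypertension among the exclusions, although its discretionary item on serious conditions could remove some women. Section 3.4 expects enough blood pressure events to make them an outcome.

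**Can the size be computed?** No. A count of women affected would need the rate of high readings, the share of those readings that the provider does not already have, and the share that staff would not mention anyway. The documents give none of the three.

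**The case against.** The strongest case on the other side has four parts.

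- **The consent form may deal with return of results.** It was not available for this review, and its absence here is not a fault in the plan. This stands as a limit. If the form sets a route, the protocol need only point to it.
- **The chart may already hold these readings.** The four measurements taken at visits are the same four named under chart review, so one fair reading is that visit vitals are entered in the chart and abstracted from it. This is possible but inferred, and a pressure stored in a chart has not thereby been brought to anyone's attention.
- **The sentence limits use and does not impose silence.** A reader might infer that the protocol forbids staff to tell a woman her pressure. The text does not support that: informing her, or advising her to see her provider, is neither diagnosis nor treatment by the study. Many staff would probably speak up. What remains is that the only written rule makes no exception and no step tells them to do so.
- **Routine care continues alongside the trial.** A reader might also take the interval between study visits as the length of time a high pressure would go unnoticed. That does not follow. If study readings trigger no action, the next study visit would not end the delay. What matters is the time to the next clinical reading, which the documents do not give and which could be short.

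**Conclusion.** The point holds as a modest patient-safety gap in the written plan and is worth a cheap correction. Section 3.1 bars clinical use of visit data, makes no exception for a high blood pressure known on the spot, and is not balanced elsewhere in the protocol by a step for passing the reading on.

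The conclusion rests on two assumptions: that the sentence on clinical use covers vital signs, as its position suggests, and that neither the consent form nor a site procedure already sets a route. The size of any harm cannot be stated. Nothing in the documents shows that any woman would in fact go untreated, and the insulin-resistance outcome, the sample size and the planned analysis are untouched.

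**What to change.** Keep the existing sentence in Section 3.1. Replacing it would also remove the no-clinical-use rule for HbA1c, lipids, glucose and insulin, and the urine dipstick, which is not the aim. Add after it:

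> Exception: a study-visit blood pressure of 140/90 mm Hg or more (with a higher limit, set by the principal investigator, for same-day referral) is told to the subject at the visit and sent to her current provider, by the same procedure in all three arms, and each notification is logged. Clinical action stays with the provider.

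If the consent form or a site procedure already covers this, refer to it instead. The 140/90 limit is proposed because it is the only blood pressure limit in the documents. There it defines an outcome, and using it as a notification trigger is a matter of judgment that the investigators may wish to set differently.

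**Cost.** One sentence of protocol text, matching consent wording if needed, and one upper limit to be chosen. Each high reading then needs a word to the woman, one message and one log entry. Staff must ask who her current provider is, since the provider contacted in hospital may no longer be the one seeing her and Section 3 expects some care outside UTMB. No visit, sample or assay is added.

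**Downside.** Notices may prompt some anti-hypertensive starts or dose increases, and Section 3.4 counts these as secondary-outcome events. A common procedure keeps the handling even across arms. The log lets the affected events be identified, though it does not remove the effect.

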### **3.2. Baseline Procedures**

Routine postpartum care will be provided by the subjects' clinical providers. Trained and experienced research staff will be responsible for all research study procedures and data abstraction.

Several data collection forms will be used during these processes. Data on these forms, devoid of personal identifiers, will be securely stored at our perinatal research division.

